**2.2 Will this research use or evaluate the safety and/or effectiveness of one or more devices?**

\* Yes

**2.2.1 Does this research study involve an evaluation of the safety and/or effectiveness of one or more devices not currently approved by the FDA for general marketing?**

\* No

[\[reviewer notes~\]](#)

**2.2.2 Does this research study involve the use or evaluation of the safety and/or effectiveness of one or more devices approved by the FDA for general marketing?**

\* Yes

**2.2.2.1 Does this research study involve an evaluation of one or more FDA-approved devices for a clinical indication, subject population, and/or operational parameter that is not specified in the current FDA-approved product labeling for that device (i.e., for an "off-label" indication)?**

\* Yes

**2.2.2.1.1 List each of the devices being evaluated for an "off-label" indication. Specify for each listed device the corresponding Investigational Device Exemption (IDE) number for this device/research study; or provide a justification for why you feel that this device and its "off-label" use, as proposed in this research study (i.e., to include potential failure of the device) constitute a non-significant risk to the involved research subjects.**

\*

Device	IDE # Non-significant risk justification
View TRANSCUTANEOUS ELECTRICAL NERVE STIMULATOR (TENS)	
The TRANSCUTANEOUS ELECTRICAL NERVE STIMULATOR (TENS) is a battery powered stimulator that is commercially available and FDA-approved for individual use at home to stimulate muscles/nerves. 1. It is not an implant. 2. It is not used in supporting or sustaining human life. 3. It does not aid in diagnosing, curing, mitigating, or treating disease. 4. It does not present a potential for serious risk to the health, safety, or welfare of a subject. TENS will be used in this study to deliver electrical stimulation via adhesive pad electrodes attached to the skin surface of the foot. The proposed use parallels the safety parameters of TENS already approved by the FDA. The investigators, Drs. [name], [name], and [name], have many years of experience with electrical stimulation and neurophysiology. They are qualified in using the TENS stimulator correctly. Furthermore, the FDA approves of TENS use at home for muscle/back pain and neuropathy. Therefore, we believe this is a non-significant risk device.

[\[reviewer notes-\]](#)

**2.3 Summarize the general classification (e.g., descriptive, experimental) and methodological design (e.g., observational, cross-sectional, longitudinal, randomized, open-label single-blind, double-blind, placebo-controlled, active treatment controlled, parallel arm, cross-over arm) of the proposed research study, as applicable.**

This is an experimental, open-label study. Both the subject and the investigator will be informed about the foot stimulation. The results obtained before and after the treatment will be compared in the same subject.

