If Yes, click Save and then [Click Here For Study Team's CITI Training Records](#) . Please ensure all personnel's training is up to date

[\[reviewer notes-\]](#)

- 1.1 Objective: What is the overall purpose of this research study?** (Limit response to 1-2 sentences.)  
To determine the effects of electrical stimulation of the nerves in the foot on the incidence of nocturnal enuresis (bedwetting) in children.
- 1.2 Specific Aims: List the goals of the proposed study (e.g., describe the relevant hypotheses or the specific problems or issues that will be addressed by the study).**  
Aim #1: To determine if foot stimulation can decrease nocturnal enuresis in children as measured by daily night-time voiding log.  
  
Aim #2: To determine if foot stimulation can improve quality of life questionnaire scores during a 6-week period, with foot stimulation applied during the third and fourth week, as measured by a validated quality of life survey.  
  
Aim # 3: Subjects who feel they are having a positive response to TENS treatment and would like to continue participation in the study for an additional 6 weeks may do so. By collecting this data for an extended period of time we hope to prove long-term efficacy and sustainability in symptom relief, and to ensure no unanticipated adverse outcomes with continued usage
- 1.3 Background: Briefly describe previous findings or observations that provide the background leading to this proposal.**  
Previous animal model studies at the University of Pittsburgh have shown a significant impact on inhibiting bladder overactivity and increasing bladder capacity with neuromodulation techniques, specifically tibial nerve stimulation ([name] et al, 2011). This has been translated into adult clinical trials through the department of urology. Through the use of a commercially available subcutaneous nerve stimulator placed on the dorsum of the foot, we were able to demonstrate a significant increase in bladder capacity and the delay of voiding sensation for up to 5 hours after stimulation in eight healthy subjects (Chen et al, 2014). This prompted the clinical trial approved under IRB PRO13020474 which is currently enrolling patients.  
  

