**2.3.1 Does this research study involve a placebo-controlled arm?**

\* No

[\[reviewer notes-\]](#)

**2.4 Will any research subjects be withdrawn from known effective therapy for the purpose of participating in this research study?**

\* No

[\[reviewer notes-\]](#)

**2.5 Will screening procedures (i.e., procedures to determine research subject eligibility) be performed specifically for the purpose of this research study?**

\* Yes

**2.5.1 List the **screening** procedures that will be performed for the purpose of this research study. Do NOT include the inclusion/exclusion criteria in this section as they will be addressed in section 3; questions 3.13 and 3.14.**

The screening procedure only includes a review of patient's medical records and performing an office based urinalysis to rule out concern for urinary tract infection. No other procedures will be performed. Patient's medical record has all the information we need to determine the idiopathic nocturnal enuresis condition. A urinalysis is normally done as part of standard of care for all office visits. The standard office visit questions, which is also available in the medical record and includes questions about neurological disorders, spinal cord injuries, and so forth will be used to rule out those who may have a neurological reason for nocturnal enuresis. Drs. [name], [name], [name], and [name] who have clinical responsibilities to the patient will review the medical records for eligibility. We also request a waive of consent for this review on section 4.7.

[reviewer notes~]

**2.6 Provide a detailed description of all research activities (e.g., all drugs or devices; psychosocial interventions or measures) that will be performed for the purpose of this research study.**

This description of activities should be complete and of sufficient detail to permit an assessment of associated risks.

At a minimum the description should include:

- **all research activities**
- **personnel (by role) performing the procedures**
- **location of procedures**
- **duration of procedures**
- **timeline of study procedures**

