**Night-time voiding log:**

The subject/parents will be instructed to record a night-time voiding log specifying the number of incontinent episodes per night. This log is included in the IRB application. Subjects/parents will fill out the log for a two week period prior to foot stimulation to determine a baseline average of nocturnal enuresis episodes, during the two week foot stimulation period to measure any acute effect on nocturnal enuresis episodes and finally during the two weeks after stimulation to evaluate any post-stimulation residual benefit.

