**3.10 What is the total number of subjects to be studied at this site, including subjects to be screened for eligibility?**

Note: The number below is calculated by summing the data entered in question 3.11. Any additions or changes to the values entered in 3.11 will be reflected in 3.10.

\* 40

**3.11 Identify each of the disease or condition specific subgroups (include healthy volunteers, if applicable) that will be studied.**

Click on the "Add" button and specify for each subgroup:

1) how many subjects will undergo research related procedures at this site; and

2) if applicable, how many subjects will be required to undergo screening procedures (e.g., blood work, EKG, x-rays, etc.) to establish eligibility. **Do Not include subjects who will undergo preliminary telephone screening.**

\*

Subgroup	Number to undergo research procedures	Number to undergo screening procedures
View Pilot study of tibial nerve stimulation	25	40

**3.12 Provide a statistical justification for the total number of subjects to be enrolled into this research study at the multicenter sites or this site.**

\* Described below:

This is a pilot study to determine if foot stimulation has any effect on nocturnal enuresis. The study is designed through the use of an objective night-time voiding log and subjective quality of life questionnaires to determine the effect of foot stimulation. As the variations on these symptom parameters is unknown, it is difficult to to determine the total number of subjects based on statistical analysis. Therefore, we decided on 25 subjects in this pilot study. Once statistical significance is reached , we will stop recruiting additional subjects in order to maintain the subject number at a minimum.

[\[reviewer notes~\]](#)

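### The one-arm analysis names no contrast that separates an effect of stimulation from drift over time, and it reads the post-stimulation weeks only as residual benefit

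*Combined protocol and SAP*

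**What the plan says.** **Design.** Section 2.3 describes an open-label study in which "Both the subject and the investigator will be informed about the foot stimulation" and "The results obtained before and after the treatment will be compared in the same subject". The answer to 2.3.1 ("Does this research study involve a placebo-controlled arm") is no.

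**Claim.** Aim 1 in section 1.2 is "To determine if foot stimulation can decrease nocturnal enuresis in children as measured by daily night-time voiding log". Section 3.12 says "This is a pilot study to determine if foot stimulation has any effect on nocturnal enuresis".

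**Periods.** Under the voiding-log heading in section 2.6, the log is kept "for a two week period prior to foot stimulation to determine a baseline average of nocturnal enuresis episodes", then during the two stimulation weeks, and "finally during the two weeks after stimulation to evaluate any post-stimulation residual benefit". Section 2.17 lists the episode counts in all three fortnights as outcome 1, with stimulation in weeks 3–4 and the post-stimulation period in weeks 5–6. Aim 2 in section 1.2 also places stimulation in the third and fourth weeks. The neuromodulation text in section 2.6 places it in the second and third.

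**Analysis.** Section 2.18 is a single line naming a t-test and ANOVA. It gives no contrast, pairing, time term, significance level or carry-over assumption.

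**The concern.** With one unblinded arm, the change from baseline to stimulation mixes any effect with natural improvement, regression to the mean, response to being studied, and declining effort with the log. The documents mention none of these.

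The difficulty is sharpened by how weeks 5–6 are labelled. If wet nights simply fall steadily, counts are lower in weeks 3–4 than at baseline and lower again in weeks 5–6. Under the plan the first fall would be taken as an acute effect and the second as residual benefit. The data best able to cast doubt on stimulation are thus assigned in advance to support it. An omnibus ANOVA over the three periods does not help, because it would flag steady drift as a difference between periods.

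At stake is a claim that stimulation reduces bedwetting when time alone could produce the result. Section 3.12 also stops recruitment once significance is reached, so drift could end the study with a positive claim.

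**Working it through.** **Nothing to reproduce.** Section 3.12 gives 25 subjects without a calculation and says the variability is unknown. What follows is illustrative.

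**Inputs from the documents:** n = 25; three 14-night periods (2.6, 2.17); entry at 4 or more episodes a month by history (3.13), roughly 2 per fortnight at the minimum.

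**Assumptions:** mean λ of 5 to 6 wet nights per 14 (also 2); at most one episode counted per night; beta-binomial counts with overdispersion 0.05; child rates with coefficient of variation 0.5; two-sided 5% test counted only in the direction of benefit (nominal 2.5%); 8,000 simulated trials per setting.

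**Contrasts.** With period means A (baseline), B (stimulation) and C (after):

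- before/after = B − A
- on/off = B − (A + C)/2

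**Linear fall d per fortnight, no effect.** A = λ, B = λ(1 − d), C = λ(1 − 2d). Before/after = −dλ. On/off = λ(1 − d) − λ(1 − d) = 0.

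Hand check at λ = 5.5, d = 0.10: the shift is −0.55. The SD of B − A is about 3.0, so the standard error is 3.0/√25 = 0.60 and the shift is 0.55/0.60 = 0.92 standard errors. With a t critical value of 2.06 (24 df), the chance of claiming benefit is about Φ(0.92 − 2.06) = Φ(−1.14) ≈ 13%. Simulation agrees:

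| Fall per fortnight | Before/after, λ = 5–6 | Before/after, λ = 2 | On/off |
|---|---|---|---|
| 5% | 6–7% | 4% | near 3% |
| 10% | 13–16% | 6% | near 3% |
| 15% | 23–29% | 9% | near 3% |

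A second model, without overdispersion and counting both directions (nominal 5%), gives 8%, 17% and 42% for before/after at λ = 2, 5 and 8 with a 10% fall. On/off stays at about 5%.

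The on/off SD is about 2.6 against 3.0, because it averages 28 off-stimulation nights.

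**Where on/off does not protect (λ = 5.5, no effect).**

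- Lasting 20% step after baseline: before/after = −0.2 × 5.5 = −1.1; on/off is half that, −0.55. False claims: 41% and 18%.
- 20% expectation response during stimulation only: both contrasts shift by −1.1, and on/off has the smaller SD. False claims: 41% and 52%. Both contrasts are significant in 37%.

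**Cost under carry-over.** For a true proportional effect e, a fraction c of which persists into weeks 5–6, on/off = −eλ(1 − c/2). With e = 0.30 and λ = 5.5 this is −1.65 with no carry-over and −0.825 with full carry-over. Power is about 73% for before/after, against 34% for on/off under full carry-over.

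**Week numbering.** With stimulation in weeks 3–4, the period centres are weeks 1.5, 3.5 and 5.5. The off periods average (1.5 + 5.5)/2 = 3.5, which matches stimulation, so a linear trend cancels. With stimulation in weeks 2–3 of six, the centres are 1, 2.5 and 5. The off periods average (1 + 5)/2 = 3, not 2.5, and the equal-weight contrast no longer cancels it.

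**The case against.** A reader might infer that the off-stimulation weeks go unused. The documents do not support that. The first fortnight is the comparator, section 2.17 includes weeks 5–6 in the three-period comparison, section 2.18 names ANOVA, and the abstract (CS2.1) compares the questionnaire across three phases. What is missing is a named contrast and a stated reading of the pattern.

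A reader might also infer that the on/off contrast is the answer to having no control group, so that a fall should be credited to stimulation only when both contrasts agree. That does not stand either. Linear drift is exactly the pattern the contrast cancels by construction. In an open-label study an expectation response during stimulation is at least as plausible, and there on/off does worse than before/after. Requiring agreement would also penalise carry-over, which the plan sets out to detect: section 2.6 looks for residual benefit "during the two weeks after stimulation to evaluate any post-stimulation residual benefit", and section 1.4 wants to explore durability in the extension. Against this, the rationale in section 1.3 is an effect lasting up to 5 hours in healthy subjects. On that rationale some return towards baseline in weeks 5–6 is a natural prediction, yet the plan never states it.

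Two further objections are fair. No document gives a drift rate or a mean of 5 to 6 wet nights, and at 2 wet nights the inflation is modest. The study is also called a pilot and openly described as uncontrolled. Neither removes the point: the stated aim is still to determine an effect, and no limit on causal interpretation is given.

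**Conclusion.** The point holds in limited form. A single open-label arm is worded to determine an effect, no contrast separates effect from drift, and weeks 5–6 are labelled so that steady background improvement counts in favour of stimulation.

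Its size cannot be fixed from the documents. Under the stated assumptions, a linear fall of 5% to 15% per fortnight raises false claims of benefit from 2.5% to between about 4% and 29%, depending on the drift and the baseline frequency. These figures are for one test at n = 25 and do not include repeated testing during recruitment.

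The on/off contrast gives partial protection. It removes a linear trend and halves a lasting step. It gives none against expectation during stimulation. Drift and carry-over cannot be told apart from these weeks without an assumption, which is why the conclusion must be limited as well as the analysis extended.

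**What to change.** 1. Reconcile the stimulation weeks in the neuromodulation text of section 2.6 with sections 1.2 and 2.17. The contrast cannot be defined until this is done; the form below is for the two-week periods listed in 2.17.
2. In section 2.18, prespecify two within-child contrasts on the episode count: stimulation minus baseline and, as supportive, stimulation minus the mean of the baseline and post-stimulation fortnights. Report both with confidence intervals. State that the second removes only a steady linear trend, only halves a lasting step after baseline, does not protect against an expectation response during stimulation, and shows half the effect under full carry-over. Do not require the two to agree; treat disagreement as inconclusive, not negative.
3. State in 2.17 or 2.18 that sustained improvement in weeks 5–6 cannot be distinguished from background improvement.
4. In sections 1.2 and 3.12, replace the aim of determining an effect with estimating the uncontrolled change during stimulation, to decide whether a controlled trial is warranted.

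The cost is a few sentences, slightly more analysis and a more modest stated conclusion. No visits, subjects or data are added, since the log already covers all three periods.

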**2.3.1 Does this research study involve a placebo-controlled arm?**

\* No

[\[reviewer notes-\]](#)

**2.4 Will any research subjects be withdrawn from known effective therapy for the purpose of participating in this research study?**

\* No

[\[reviewer notes-\]](#)

**2.5 Will screening procedures (i.e., procedures to determine research subject eligibility) be performed specifically for the purpose of this research study?**

\* Yes

**2.5.1 List the **screening** procedures that will be performed for the purpose of this research study. Do NOT include the inclusion/exclusion criteria in this section as they will be addressed in section 3; questions 3.13 and 3.14.**

The screening procedure only includes a review of patient's medical records and performing an office based urinalysis to rule out concern for urinary tract infection. No other procedures will be performed. Patient's medical record has all the information we need to determine the idiopathic nocturnal enuresis condition. A urinalysis is normally done as part of standard of care for all office visits. The standard office visit questions, which is also available in the medical record and includes questions about neurological disorders, spinal cord injuries, and so forth will be used to rule out those who may have a neurological reason for nocturnal enuresis. Drs. [name], [name], [name], and [name] who have clinical responsibilities to the patient will review the medical records for eligibility. We also request a waive of consent for this review on section 4.7.

[reviewer notes~]

**2.6 Provide a detailed description of all research activities (e.g., all drugs or devices; psychosocial interventions or measures) that will be performed for the purpose of this research study.**

This description of activities should be complete and of sufficient detail to permit an assessment of associated risks.

At a minimum the description should include:

- **all research activities**
- **personnel (by role) performing the procedures**
- **location of procedures**
- **duration of procedures**
- **timeline of study procedures**

**Night-time voiding log:**

The subject/parents will be instructed to record a night-time voiding log specifying the number of incontinent episodes per night. This log is included in the IRB application. Subjects/parents will fill out the log for a two week period prior to foot stimulation to determine a baseline average of nocturnal enuresis episodes, during the two week foot stimulation period to measure any acute effect on nocturnal enuresis episodes and finally during the two weeks after stimulation to evaluate any post-stimulation residual benefit.

**Neuromodulation:**

In the office to calibrate TENS device - skin surface electrodes will be attached to the bottom of one foot for electrical stimulation. The stimulator and electrodes are FDA-approved devices for TRANSCUTANEOUS ELECTRICAL NERVE STIMULATION (TENS) and are commercially available. The stimulation characteristics include a continuous frequency of 5 Hz, pulsewidth 0.2 ms, and intensity 2-4 times the threshold voltage required for inducing

toe twitching - or the intensity that the subject feels comfortable with. The subjects will also be instructed how to use the stimulator and where to attach the electrodes on the foot at the beginning of the study. The investigator will provide the stimulator and electrodes. The subjects will be asked to wear socks to prevent the electrodes from detachment and to stop the stimulation during walking or in any non-resting situation. Subjects will be provided a TENS device and disposable foot pads for two weeks of treatment. Subjects will be asked to use the stimulator for a MINIMUM of 60 minutes in the evening prior to bedtime at home for two weeks. They will be encouraged to use the stimulator for more time than the minimum as long as they accurately record the total duration. Stimulation will be performed during the second and third weeks of the study only.

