**T3.1**

**Why do you feel that all aspects of this research study, including screening and follow-up, involve no more than minimal risk to the research subjects?**

Trans-cutaneous Electrical Nerve Stimulation (TENS) devices are FDA approved and commercially available to treat a variety of clinical conditions including pain (migraines, musculoskeletal pain and labor pain). The only reported side-effects are local irritation from electrode pads and minor cramping of stimulated muscles. Many studies have evaluated the use of TENS devices for parasacral neuromodulation in children with no serious adverse events reported.

The voltage used for the TENS device will be only as high as is required to stimulate an involuntary muscle contraction of at least two toes. In various trials in adults this voltage very rarely corresponds to any actual discomfort to the patient. If during the trial stimulation at the time of enrollment in the office, the child demonstrates an intolerance to this stimulation due to discomfort, he/she will be excluded from the study.

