#### TENS Unit Training:

The training session will take place in a patient room in the office of pediatric urology. The training will be conducted in person by [name] with the parent(s) and child in the room. [name] will explain the device, how it works and how to use it to the parent(s) along with a detailed user manual that is provided with the stimulator. The parent(s) will be instructed how to place the stimulation pads on the child's foot (most distal covering the planar bridge of the foot and more proximal pad over the medial edge of the foot). The parent(s) will then be instructed on how to connect the two electrode wires to the device and turn it on. The device settings are preprogrammed at time of sale, so no frequency change adjustments need to be made. The parent(s) will incrementally increase the voltage on the device until the child elicits a response of involuntary contraction of at least two toes of the foot including the great toe. Stimulation will be continuous for 5 minutes assessing the child's comfort level. If the child is obviously uncomfortable at the level of voltage required for involuntary motor movement and does not perceive they would be able to stimulate in this fashion at home for periods of up to one hour, they will not be eligible for the study.

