**45 CFR 46.407**

- The risk is justified by the anticipated benefit to the subjects; and the relation of the anticipated benefit to the risk is at least as favorable to the subjects as that presented by available alternative approaches.

Provide a justification which **must address all considerations** related to the designated category of research:

At stated prior we feel this study provided minimal risk based on the rarity and minority of side effects from previous TENS studies in adults. We will use a voltage only high enough to elicit an involuntary twitch of the toes, which is generally non-painful.

Although the electrical stimulation may help subjects with nocturnal enuresis, this benefit is not known or guaranteed. However, information learned from this study will help investigators learn how to better treat children with nocturnal enuresis in the future.

[\[reviewer notes-\]](#)

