**5.1.1 Describe the steps that will be taken to prevent or to minimize the severity of the potential risks:**

To minimize foot cramping, the lowest threshold voltage required (to induce spontaneous movement of the toes) will be used for actual stimulation. To minimize the risks, the research procedures will be conducted by experienced personnel. The subjects will be appropriately trained on how to use the TENS stimulator and attach the electrodes. The subjects will also be told that they can call the investigators anytime with any questions or problems.

**5.2 What steps will be taken in the event that a clinically significant, unexpected disease or condition is identified during the conduct of the study?**

\* **Addressed below:**

The study will be stopped immediately in the event that a clinically significant, unexpected condition is identified. The subject will also be referred to appropriate care for the unexpected condition.

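### Section 2.6 allows stimulation at 2-4 times the toe-twitch threshold, while the risk sections describe only the voltage needed to move the toes

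*Combined protocol and SAP*

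**What the plan says.** Section 2.6, under Neuromodulation, specifies "intensity 2-4 times the threshold voltage required for inducing" "toe twitching - or the intensity that the subject feels comfortable with". The paragraph begins with calibration in the office and goes on to home use.

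Three risk sections describe the voltage differently:

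- T3.1 (minimal-risk rationale): the voltage "will be only as high as is required to stimulate an involuntary muscle contraction of at least two toes". It adds that in adult trials "this voltage very rarely corresponds to any actual discomfort to the patient", and excludes a child if at the office trial "the child demonstrates an intolerance to this stimulation due to discomfort".
- Section 3.5.5 (justification of the permitted category for children): "We will use a voltage only high enough to elicit an involuntary twitch of the toes", a level it calls generally free of pain.
- Section 5.1.1 (risk minimisation, as the measure against foot cramp): "the lowest threshold voltage required (to induce spontaneous movement of the toes) will be used for actual stimulation".

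The TENS Unit Training text in section 2.6 has the parent raise the voltage until there is "involuntary contraction of at least two toes of the foot including the great toe". The child's comfort is then assessed over 5 minutes. A child who is uncomfortable at the motor-response voltage and does not expect to manage at home is ineligible. Section 3.14 excludes children who do not tolerate this session.

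**The concern.** A multiple of a threshold and the threshold itself are different exposures. The difference matters because voltage is an express ground for calling the study minimal risk in children from age 5. The adult comfort experience in T3.1 and the statement about pain in 3.5.5 both concern the level that moves the toes, not a multiple of it. The precaution against cramp in 5.1.1 is also the threshold voltage.

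Someone assessing risk from section 2.6 and someone assessing it from section 5.1.1 would have different exposures in mind. Nor could either say which intensity a child would receive. Section 5.13 foresees adjusting device settings after a telephone call during the extension, so staff also need a single statement to work from.

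**Working it through.** The plan states no figure to reproduce, so the check is a comparison of the texts followed by simple ratios.

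**1. The statements side by side.** Let T be the voltage at which the toes first twitch.

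| Place | Response named | Level stated |
|---|---|---|
| 2.6 Neuromodulation | toe twitch | 2T to 4T, or a comfortable level with no numeric bound |
| 3.5.5 | toe twitch | just enough for the response |
| 5.1.1 | toe movement | lowest threshold, for actual stimulation |
| T3.1 | contraction of at least two toes | no more than the response needs |
| 2.6 TENS Unit Training | contraction of at least two toes, including the great toe | raised until the response occurs |

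**2. Same response: 2.6 against 3.5.5.** Both name the twitch, so 3.5.5 describes 1T. The ratio to the level in 2.6 is 1T/2T = 50% at the lower end and 1T/4T = 25% at the upper end. This needs no outside assumption. The same ratios apply to 5.1.1 if toe movement and toe twitch share one threshold.

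**3. Different response: T3.1 and the training text.** A contraction of two toes may need more voltage than a first twitch. Suppose it needs k times T. The documents do not give k; I assume a range of 1 to 2. The described level as a share of the level in 2.6 runs from k/2 (against 2T) to k/4 (against 4T):

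| k (assumed) | Share of 2T | Share of 4T |
|---|---|---|
| 1 | 50% | 25% |
| 1.25 | 62.5% | 31.25% |
| 1.5 | 75% | 37.5% |
| 2 | 100% | 50% |

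The two-toe level reaches the bottom of the range in 2.6 only if k is at least 2, and the top only if k is at least 4.

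**4. Can another reading remove the conflict?**

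- Calibration versus treatment: no. Section 5.1.1 speaks of actual stimulation, so the threshold statement is not confined to calibration.
- The comfort clause: no. It is joined by *or*, so 2-4 times threshold remains a permitted setting. The clause may be a step down for children who do not tolerate the multiple, or it may allow more. No ratio can be computed for it.
- A single value hidden in the range: no. A range whose ends differ by a factor of two cannot equal one minimum level.

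**5. The tolerance screen.** The training text describes tolerance only at the level that produces the motor response and mentions no step to a higher multiple. Since the Neuromodulation paragraph opens with office calibration, a child might meet a higher level there, but the training text does not say so.

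**The case against.** The strongest reply is that the conflict concerns one branch of an alternative. A child who is comfortable at the toe-movement level and is stimulated there satisfies every section at once, so the plan permits 2-4 times threshold without requiring it. That is correct and limits the claim: it does not follow that every child would receive more than the risk sections describe. It does not remove the contradiction, because the risk sections say the voltage will go no higher than the toe response needs, and section 2.6 lets it go higher.

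Second, T3.1 and the training text name a two-toe contraction, so the size of the gap is unknown there and could vanish at the bottom of the range. This stands; the firm ratios belong to 3.5.5 and, under the shared-threshold assumption, 5.1.1. A voltage ratio is also not a measure of discomfort or harm.

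Third, section 3.14 names no voltage, and calibration above threshold in the office is a possible reading. A gap in screening is therefore not proved; what is shown is that the described screen stops at the motor response.

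Fourth, the risk case has other supports:

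- a marketed device with minor reported effects (T3.1), and a non-significant-risk argument that does not rest on voltage (2.2.2.1.1);
- cramp and skin effects disclosed as common risks (5.1);
- contact with the investigators at any time (2.6, 5.1.1);
- discontinuation for intolerance (5.7), and a tolerability call in the extension (5.13).

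These remain, and no demonstrated harm is claimed. They do not tell the reader which intensity is planned.

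**Conclusion.** The concern holds. Section 2.6 contradicts sections 3.5.5 and 5.1.1 on stimulation intensity and cannot be squared with the wording of T3.1. Where the response named is the same, the risk text describes 50% to 25% of the voltage that 2.6 allows. For the two-toe contraction the share is 50% to 25% at k = 1, rising to 100% to 50% at k = 2, with k an assumption.

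The contradiction itself depends neither on k nor on how the comfort clause is read. It should be fixed before the plan is relied on, because the voltage part of a paediatric minimal-risk justification describes a lower exposure than the procedures permit. The endpoints, the analysis and the sample size do not depend on this text.

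**What to change.** Reconcile T3.1, both parts of section 2.6 (Neuromodulation and TENS Unit Training), 3.5.5 and 5.1.1 so that one intensity statement appears throughout. Name the same toe response each time and say what the comfort clause is for. Then check that the risk justification, the cramp precaution and the tolerance-screen text match that statement. The choice of intensity and of any screening rule belongs to the investigators and the IRB; none is proposed here.

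One small mismatch can be settled in the same edit: the training text treats one hour as the most a child would need to manage at home, while the Neuromodulation text makes 60 minutes the least. These should also be reconciled.

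Optionally, if the voiding log (an attachment not shown) does not already do so, record each child's threshold and home setting alongside duration, so that the intensity delivered can be reported.

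The reconciliation costs wording changes in five places, with no extra patients or visits. The optional recording adds one or two data fields. Any change to the screen that the investigators or the IRB might decide on would be a separate cost.
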